#### **5.4.2 Withdrawal from the Trial**

Patients may withdraw from the trial at any time without giving a reason. Withdrawal of consent will be considered withdrawal from the trial. The Investigator should make every attempt to clarify the level of withdrawal: eg, whether or not banked samples can still be retained and evaluated, if the patient can still be contacted by phone for checking his/her status (eg, alive or not), or to return for safety visits. In case of withdrawal from the trial for reasons other than consent withdrawal, the assessments scheduled for the early termination visit should be performed immediately and return for a Safety/Follow-up visit 4 weeks after the last dose of IMP. Patients will return for an additional safety visit 4 months after the last dose of IMP. In any case, the appropriate CRF section must be completed. Patients will be asked to confirm that any samples collected but not yet analyzed can be utilized.

Patients withdrawn from IMP will continue the safety and immunogenicity follow-up until the end of the trial (also see Section 5.4.1 for specific details). These patients will be managed based on the Investigator's clinical judgment and per local guidelines, and any new medication prescribed in such a period will be recorded. In any case, the appropriate case report form (CRF) section must be completed.

## 5.5

### Premature Termination of the Trial

The clinical trial may be terminated prematurely or suspended at the request of Health Authorities or if new safety or efficacy information leads to an unfavorable risk benefit judgment. The Sponsor may discontinue the trial if it becomes unjustifiable for medical or ethical reasons, for poor enrollment, or because of discontinuation of clinical development of MSB11022 or withdrawal of Humira® from the market.

Health Authorities and Independent Ethics Committees (IECs)/Institutional Review Boards (IRBs) will be informed about the discontinuation of the trial in accordance with applicable regulations.

## 5.6

### Definition of End of Trial

The end of the trial is defined as the last patient's end of trial visit.

## 6

### Investigational Medicinal Product and Other Drugs Used in the Trial

The term "IMP" refers to an active substance or a placebo being tested or used as a reference therapy in a clinical trial, including products that have a marketing authorization but are packaged or administered differently from the authorized form, used for an unauthorized indication, or used to gain further information about the authorized form.

## 6.1

### Description of the Investigational Medicinal Product

CCI [REDACTED]

[REDACTED]

[REDACTED]

[REDACTED]

[REDACTED]

[REDACTED]

[REDACTED]

## 6.2

### Dosage and Administration

MSB11022-CCI [REDACTED] will be administered at a dose of 40 mg s.c. every other week starting from baseline up to and including Week 48.

The Humira® will be administered at a dose of 40 mg s.c. every other week starting from baseline up to and including Week 48.

### 6.3 Assignment to Treatment Groups

A patient is eligible for randomization only if he/she fulfills all the inclusion criteria and none of the exclusion criteria and their eligibility is confirmed on Day 1/Week 0. The patient will be randomized by a central IWRS on Day 1/Week 0 after all eligibility criteria are confirmed in a 1:1 ratio to receive MSB11022-CCI or Humira® in a double-blind manner. Randomization will be stratified by the type of systemic therapy previously received.

A treatment kit labeled with individual kit/medication numbers will be provided to each trial site. See Sections 6.9 and 6.10 for methods of blinding and emergency unblinding. In the event of change in the reference product and the further supply is not guaranteed, the sponsor will have an established process to avoid any bias in the blinding. The IMP will be administered every other week. The IMP will be administered at the site at the visits indicated in the Schedule of Assessments after all assessments have been completed and the patient is determined to be eligible to remain in the trial. At each visit when IMP is dispensed, the trial staff will contact the IWRS after the Investigator confirms that the patient has met the criteria to continue in the trial to obtain appropriate kit numbers, and the specified kits will then be dispensed.

### 6.4 Concomitant Medications and Therapies

All concomitant medications taken by the patient during the trial, from the date of signature of informed consent are to be recorded in the appropriate section of the CRF, noting the name, dose, duration, and indication of each drug. Nondrug interventions and any changes to a concomitant medication or other intervention should also be recorded in the CRF.

#### 6.4.1 Permitted Medicines

Permitted medicines will not be provided by the sponsor as they are considered standard of care background medications.

It is important that medication dosages taken during the study period remain stable. This includes, but it is not limited to, the dosage of corticosteroids and NSAIDs. However, reductions in these treatments will be allowed as clinically required for safety reasons.

**Methotrexate:** All patient should maintain a stable MTX dose (10 to 25 mg/week, PO, IM, or SC) during the study period. Any modification of the route of administration is not allowed. However, a dose reduction of MTX will be allowed in case of AEs. Temporary interruptions administration are allowed for up to 14 days (can be interrupted up to twice because MTX is administered once weekly). See withdrawal criteria related to interruptions in Section 5.4.1.

**Folic Acid:** It is possible that certain AEs that are commonly associated with MTX treatment occur. In order to minimize MTX toxicity, all patients treated with MTX should receive folic acid or equivalent at a dose of at least 5 mg/week according to local guidelines. This can either be given

as a single dose weekly or be divided into daily doses to achieve at least 5 mg folic acid per week. It is the Investigator's decision as to which dosing regimen is used.

**Hydroxychloroquine or chloroquine:** as per inclusion and exclusion criteria.

Oral corticosteroids ( $\leq 10$  mg/day prednisone or equivalent) and NSAIDs are permitted during the study.

**NSAID:** patients may be treated with NSAIDs (including low dose aspirin and COX-2 inhibitors) for symptomatic treatment of their arthritis up to the maximum recommended dose per local labeling throughout the study (including COX-2 inhibitors). Drug must be at a stable dose for at least 2 weeks prior to baseline. Increases in the NSAID dose during the study are not allowed. However, discontinuation or reduction is allowed in case of NSAID-related toxicity. In patients who receive NSAIDs, prophylactic treatment with proton pump inhibitors or H2-receptor blockers is recommended.

NSAIDS, up to the maximum recommended dose per local labeling, are also allowed for the management of AEs not related to RA such as colds or sprains throughout the study (including COX-2 inhibitors).

Analgesics (other than NSAIDs) up to the maximum recommended doses may be used for pain control as required except for high potency opioids as delineated below. However, patients should not take analgesics within 12 hours prior to a visit where clinical efficacy assessments are performed.

Any medications that are considered necessary to protect patient welfare and will not interfere with the IMP may be given at the Investigator's discretion.

Rescue medications may be administered to address ineffective treatment, anticipated adverse reactions, or anticipated emergency situations.

Any concomitant medications (including over-the-counter medications, herbal medications, preventive vaccines, vitamins, and food supplements) and procedures must be recorded. A description of the type of drug or procedure, the amount, duration, reason for administration of drug, and the outcome of any procedure must be documented. AEs related to the administration of a concomitant medication or the performance of a procedure must also be recorded.

#### **6.4.2 Prohibited Medicines**

The use of prohibited medications will require the patient to be withdrawn from the IMP.

All biological and non-biological DMARDs other than MTX and hydroxychloroquine or chloroquine are prohibited during the study and must be discontinued prior to the initiation of IMP in accordance with specifications as per the inclusion and exclusion criteria.

High potency opioid analgesics (eg, methadone, hydromorphone, oxycodone, fentanyl, or morphine) as per the inclusion and exclusion criteria.

**Intravenous, intramuscular or intra-articular corticosteroids:** Intravenous or intramuscular corticosteroids are not permitted during the study. Intra-articular corticosteroids are not permitted within 6 weeks prior to baseline. Injection of intraarticular steroids while on blinded study medication is discouraged, but may be used in a limited fashion. No more than 1 joint per 24-week period may be injected during the core period of the study and should not be given 8 weeks or less before the Week 24 visit. No single injection should exceed 40 mg of triamcinolone (or equivalent).

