## **5.4 Criteria for Patient Withdrawal**

### **5.4.1 Withdrawal from Trial Therapy**

A patient will no longer receive the study medication in the event of any of the following circumstances:

- a. Any events that unacceptably endanger the safety of the patient, including but not limited to the following:
  - Use of prohibited treatment that in the opinion of the Investigator or Sponsor necessitates the patient treatment to be interrupted
  - Occurrence of an exclusion criterion that is clinically relevant and affects the patient's safety, if discontinuation is considered necessary by the Investigator and/or Sponsor
  - Anaphylactic or other serious allergic reactions
  - Development of active or latent TB
  - New or worsening symptoms of congestive heart failure
  - Biopsy confirmation of any malignancy other than non-melanoma skin cancer, such as basal cell carcinoma and squamous cell carcinoma.
  - Symptoms suggestive of lupus-like syndrome
  - Pregnancy
- b. Interruption of MTX more than twice in a period of 4 weeks, or for a period of interruption longer than 4 months.

- c. Noncompliance or protocol violations that in the opinion of the Investigator or Sponsor necessitates the patient being withdrawn. The decision to withdraw the patient should be taken in consultation with the Medical Monitor.
- d. Participation in any other trial during the duration of this trial.
- e. If the whole trial is discontinued prematurely.
- f. Lost to follow-up.

If a patient is lost to follow-up, every possible effort must be made by trial center personnel to contact the patient and determine the reason for discontinuation. The measures taken to follow-up must be documented. If a patient discontinues before completion of trial procedures, the reason for discontinuation must be documented in the CRF and source documents.

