10.1 Definition of Protocol Deviations

Protocol deviations occurring during the study will be determined for all enrolled subjects, mainly from the clinical database by either clinical and/or medical review processes, and entered into the Clinical Trial Management System (CTMS).

The mapping of the protocol deviations from the CTMS to analysis will be performed as per the table below:

PD Guidance	CTMS	SAP	SDTM	ADaM	
Minor	Minor	Not required	Not included	Not included	
Important	Major	Important	Important - flagged with PDEVXXX code	Important - flagged with PDEVXXX code	
Priority (subset of Important)	Critical (subset of Major)	Important	Mapped to Important	Mapped to Important	
NA	NA	Clinically Important (lead to exclusion from PP pop)	flagged with PDEVXXX code	additional flag = Y/N in ADDV (may also include conditions not considered to be PD's)	

Important protocol deviations are protocol deviations that might significantly affect the completeness, accuracy, and/or reliability of the study data or that might significantly affect a subject's rights, safety, or well-being.

Important protocol deviations may also be recorded as 'major' protocol deviations in the CTMS but will presented only as important in the analysis output.

Important protocol deviations include:

- Subjects that are dosed on the study despite not satisfying the entry criteria;
- Subjects that develop withdrawal criteria whilst on the study but are not withdrawn;
- Subjects that receive the wrong treatment or an incorrect dose;
- Subjects that receive an excluded concomitant medication;
- Deviation from Good Clinical Practice (GCP).

Clinically Important Protocol Deviations are a subset of important protocol deviations which lead to the exclusion of a subject from the Per-Protocol (PP) analysis set.

The following deviations will be identified and confirmed prior to the partial database lock for the final analysis.

- Important protocol deviations including
 - Deviations from the inclusion and exclusion criteria
 - Deviations post inclusion

Protocol deviations may be identified by the data-managers, clinical and medical staff either by programmed validation checks or data listings/reports or manual verification of data sources.

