11.1 Descriptive Methods

Descriptive statistics for continuous data will include the following:

- Number of subjects with non-missing data (n)
- Number of subjects with missing data
- Mean, standard deviation (SD)
- Median, first and third quartiles (Q1 and Q3)
- Minimum and maximum
- 95% confidence interval (CI).

All statistics will be rounded according to Merck's Global Biostatistics Output Standards (GBSOS) Booklet (Version 4.0 or later), ie, percentages will be rounded to one decimal. The mean, median, Q1, Q3, and 95% CI will be presented with one additional decimal compared to the raw data; SD will be presented with two additional decimals compared to the raw data; and minimum and maximum will be presented with the same number of decimals as the raw data.

All data will be presented by nominal visit (including the safety follow-up visits – four weeks and four months after the last dose of IMP) and no visit windowing rules will be implemented. Data from unscheduled visits will be listed but will not be included in summaries presented by

visit. The exceptions will be in the calculation of the baseline values. Data from unscheduled visits will also be included in the calculation of the worst on-treatment values and grades.

Categorical data will be summarized by presenting the number of subjects with non-missing data (n), the number of subjects with missing data (missing), and the number and percentage of subjects in each category. Percentages will be based on the number of subjects with non-missing data in the analysis set of interest, unless otherwise specified.

Time to event variables will be summarized by presenting Kaplan Meier estimates and 95% CIs.

Change from baseline will be calculated as the post-baseline value minus the baseline value. Percent change from baseline is defined as (100 x (post-baseline – baseline) / baseline).

If all baseline values are missing for a particular variable, the change from baseline and percent change/percent improvement from baseline will not be calculated.

A 2-sided significance level of 5% will be used for all analyses. Two-sided 95% confidence intervals will be calculated.

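### Protocol 6.4.2 makes stopping study drug mandatory after prohibited medication, Protocol 5.4.1(a) leaves it to opinion, and nothing says which rule prevails

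*Protocol*

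**What the plan says.** Protocol 6.4.2 (Prohibited Medicines) opens with a rule that leaves no discretion: "The use of prohibited medications will require the patient to be withdrawn from the IMP".

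Protocol 5.4.1 (Withdrawal from Trial Therapy) lists the circumstances in which study drug stops. Under item (a), events that endanger the patient, the entry on this trigger is conditional: "Use of prohibited treatment that in the opinion of the Investigator or Sponsor necessitates the patient treatment to be interrupted". Item (c) also makes withdrawal for protocol violations a matter of Investigator or Sponsor opinion and adds consultation with the Medical Monitor.

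The only pointer from Protocol 6.4 to the 5.4.1 withdrawal criteria concerns methotrexate interruptions.

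After study drug stops there is an Early Termination visit, and then, under Protocol 5.4.2, "Patients withdrawn from IMP will continue the safety and immunogenicity follow-up until the end of the trial".

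The SAP reports data by nominal visit, and "no visit windowing rules will be implemented" (SAP 11.1). The same section sets the default denominator: "Percentages will be based on the number of subjects with non-missing data in the analysis set of interest, unless otherwise specified". SAP 11.4.1 repeats the ITT analysis of Week 12 ACR20 with missing values set to non-response, and adds a version that imputes non-response for premature discontinuation before Week 12. Neither version has a rule for a patient who takes a prohibited drug and stays on study drug.

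**The concern.** Sites and the sponsor have two instructions for the same event, one mandatory and one discretionary. Two patients who take the same prohibited drug at the same time could be handled differently, with both decisions defensible from the text.

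The choice carries into the results in two places. Treatment discontinuations, which SAP 12.1 tabulates by reason, would partly reflect which section was followed. Week 12 ACR20, the key secondary endpoint, would be scored differently for the same clinical event. One patient would be missing or a non-responder. The other would be scored on observed data that may include response to, for example, a second DMARD.

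**Working it through.** **Step 1: trace one patient through both rules.** Take a patient who uses a prohibited DMARD before Week 12.

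- *6.4.2 followed.* Study drug stops, the Early Termination visit takes place, and safety and immunogenicity follow-up continues. Early Termination data carry their own visit label and, without windowing, do not become Week 12 data. Week 12 ACR20 is therefore usually missing. The patient is out of the unimputed ITT denominator and is a non-responder in the non-responder analysis.
- *5.4.1(a) followed, stopping judged unnecessary.* The patient attends Week 12 and is scored as observed in every ITT version.

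**Step 2: size.** The documents give neither a rate of prohibited-medication use nor an expected ACR20 rate. Inputs:

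- n = 130 per arm (Protocol 8.1).
- Assumption: k = 1 to 5 affected patients, all in one arm, all responders if kept on drug.
- Assumption: ACR20 of 50%, 60% or 70% if all are kept (r = 65, 78, 91).

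Formulas: kept = r/n; non-responder = (r − k)/n; unimputed = (r − k)/(n − k).

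| ACR20 if kept | k | Non-responder scoring | Unimputed |
|---|---|---|---|
| 65/130 = 50% | 1 | 64/130, −0.77 points | 64/129, −0.39 |
| | 5 | 60/130, −3.85 | 60/125, −2.00 |
| 78/130 = 60% | 1 | 77/130, −0.77 | 77/129, −0.31 |
| | 5 | 73/130, −3.85 | 73/125, −1.60 |
| 91/130 = 70% | 1 | 90/130, −0.77 | 90/129, −0.23 |
| | 5 | 86/130, −3.85 | 86/125, −1.20 |

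If the five would have been non-responders when kept, stopping them leaves the non-responder analysis unchanged and raises the unimputed rate. At 70% that is 91/125 = 72.8%, or +2.8 points; at 50% it is 65/125 = 52.0%, or +2.0 points.

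**Step 3: compare with the precision of the difference.** SAP 15.2.1 specifies the Newcombe interval. With equal observed rates and 130 per arm, its half-width is √[(p − l)² + (u − p)²], where l and u are the Wilson limits of one arm. This gives 11.98 points at 50%, 11.75 at 60% and 11.04 at 70%. At 60% with k = 5 in one arm, the difference is −3.85 points (95% CI −15.6 to 8.1) under non-responder scoring and −1.60 points (−13.5 to 10.3) unimputed. Equal numbers in both arms would largely cancel.

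**Step 4: discontinuations.** Each patient stopped rather than kept adds 100/130 = 0.77 points to the arm's discontinuation rate. The planned drop-out is 0.20 × 130 = 26 patients per arm.

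**The case against.** The strongest reply is that the two rules can coexist. The 5.4.1(a) entry sits in a non-exhaustive list of safety stops. Some treatments are disallowed outside 6.4.2, such as NSAID dose increases and oral steroids above 10 mg/day (Protocol 6.4.1) or live vaccines (exclusion criterion 12). Discretion could be meant for those, leaving 6.4.2 absolute for its own list. That reading is coherent, but the protocol does not state it, and a site that turns to 5.4.1 for withdrawal rules finds discretion with no reference to 6.4.2.

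Other parts of the reply limit what can be claimed. A reader might infer any of the following, and the documents do not support them:

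- *Stopping is purely a site matter.* Section 5.4.1(a) gives the opinion to the Investigator or the Sponsor, and 5.4.1(c) brings in the Medical Monitor.
- *Limited intra-articular steroid use triggers mandatory stopping.* Section 6.4.2 itself allows it: "Injection of intraarticular steroids while on blinded study medication is discouraged, but may be used in a limited fashion". Protocol 7.3.1.1 records an injected joint as not done for 12 weeks and then lets it be assessed again, which presupposes that the patient continues.
- *The rescue sentence opens a route to prohibited drugs.* "Rescue medications may be administered to address ineffective treatment, anticipated adverse reactions, or anticipated emergency situations" stands under Permitted Medicines. A general permission does not naturally override the specific bans in 6.4.2.
- *The deviation tables would differ materially.* SAP 10.1 lists "Subjects that develop withdrawal criteria whilst on the study but are not withdrawn" as an important deviation, and whether it applies depends on which section governs. Receipt of an excluded medication is an important deviation under either reading, so the class is the same. Per-protocol exclusion rests on SAP Appendix I, which is not in the text available here, so nothing is claimed about that set.
- *Week 12 ACR20 is necessarily missing after a stop.* Efficacy assessments after stopping are not required, but they are not forbidden either.

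**Conclusion.** The inconsistency is in the current protocol text, and the SAP does not resolve it. It is a minor point. Under non-responder scoring each affected patient moves an arm by at most 0.77 points. Five in one arm, all responders if kept, move it by 3.85 points, about a third of the CI half-width. The unimputed analysis moves less in that case (0.2 to 2.0 points across the table). These sizes rest on the assumed counts and response rates.

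ACR20 is descriptive here, with no margin or test, so no formal decision turns on it. A reader might infer a biased comparison between arms. Blinding gives no reason to expect the handling to differ by arm. A reader might also infer an effect on the primary endpoint. Stopping shortens a patient's exposure, but the rule for counting patients with an AESI is the same under both readings. Confidence is high on the textual mismatch and lower on the scoring consequence, because a missing Week 12 value is the usual rather than the certain result.

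**What to change.** (a) Make Protocol 5.4.1(a) and 6.4.2 agree by cross-reference. Withdrawal from study drug is mandatory for prohibited biological or non-biological DMARDs. For other disallowed products, for example a short opioid course, the Investigator or Sponsor decides with the Medical Monitor. Mandatory stopping for every listed product is a debatable alternative: one emergency opioid dose would end treatment in a safety trial that wants 200 patients at Week 52.

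(b) In the SAP 11.4.1 non-responder analysis, also count as non-responders patients who took a prohibited DMARD, or an IV or IM corticosteroid given for RA, before the Week 12 assessment, whether or not study drug was stopped. The limit to RA matters for the steroids: otherwise an IV steroid given for an allergic reaction would count as failure of RA treatment.

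Cost: a sentence in each of the two protocol sections, one SAP line, and one programming rule. No new data are needed, because concomitant drugs and the reason for each are already recorded (Protocol 6.4.1). The ACR20 rate in that one analysis may be slightly lower.
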